4. STUDY POPULATION

POPULATION

Patients aged 65 years or older with displaced completely intra-articular distal radius fractures (AO type C).

Inclusion criteria:

- ≥65 years at time of trauma
- Intra-articular distal radius fracture (AO type C*)
- One or more of the following fracture characteristics within 3 weeks post-trauma (including secondary dislocation):
 - ≤15° inclination
 - ≤5 mm radial length
 - >15° dorsal tilt
 - >20° volar tilt
 - intra-articular gap or step-off >2 mm
(This will be measured by 1 researcher)
- < 3 weeks post trauma
- Living independent at home (e.g. not in a retirement home)
- Fit for surgery
- Mentally competent
The patient must be able to fully understand the consequences of participation. This includes that the patient must be aware of the burden that the research project provides, the possible complications in both treatment arms and the possibility to not participate in the trial. Furthermore he or she must be able to fill out the questionnaires.
- Dutch fluency and literacy
- Informed consent

Exclusion criteria:

- Open fractures
- Neurovascular damage
- Multiple-trauma patients (ISS >16)
- Other fractures in the injured extremity other than ulnar styloid process fractures
- Simultaneous fracture of the contralateral forearm
- Previous fracture of the ipsilateral radius resulting in a malunion or an impaired function

*Classifications will be made based on posterior-anterior (PA) and lateral radiographs. When in doubt about articular involvement CT images can be acquired by the treating physician.

SAMPLE SIZE CALCULATION

The study will be a non-inferiority study. Sample size calculation is based on a power of 90%, an alpha of 0.025, a standard deviation of 23 points and a minimal important change of 14 points based on the PRWE^{12,25} as primary outcome measure after 1 year. In addition we take into account that outcome data will be correlated within 19 participating centers with an ICC of 0.1. We calculated that with 20% loss to follow-up after 12 months, 57 patients are needed per group in this non-inferiority trial. This means 114 patients need to be included.

FEASIBILITY

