5. TREATMENT OF SUBJECTS

ALL GROUPS

Study procedures:

Patients with an intra-articular fracture (AO type C) who meet the above mentioned inclusion criteria are eligible for the study. The surgeon on duty or the emergency physician is responsible for this initial screening.

In each eligible patient the surgeon on duty or the emergency physician will initially attempt to reduce the fracture after which the patient receives a temporary below-elbow forearm cast. For this, participating hospitals may use their preferred technique. Also they may follow their local protocol for anesthetics.

Preferably, eligible patients will receive information about the study at the emergency department.

One week after trauma they will be seen at the outpatient clinic. They can sign an informed consent form if they agree to participate up to 3 weeks after trauma.

Upon obtaining informed consent, patients will be randomized into either the surgical intervention group (open reduction and internal fixation) or the control group (closed reduction and plaster immobilization). For both treatment arms, participating hospitals may use their preferred technique. Also they may follow their local protocol for anesthetics, duration of cast treatment and vitamine C prescription. These data will be collected to correct for during data analysis.

In order to avoid any imbalance between treatment groups, patients will be randomized in 2 strata using a block randomization. Two strata according to age: 65-75 and 75 and older.

At baseline characteristics will be collected such as sex, side, dominant hand, trauma mechanism and the frailty questionnaire (frailty score <1 week after trauma).

Post-treatment patients will be seen at the outpatient clinic according to the regular protocol. These visits are also used for the follow-up assessments. Data is collected at 1 week, 3 weeks, 6 weeks, 3 months, 6 months, and 12 months. After 6, 9 and 12 months depending on the treating physician's and/or patients' preference they can visit the hospital or can be visited at home.

The Patient-Rated Wrist Evaluation score (PRWE), the Disability of the Arm, Hand and Shoulder (DASH), Quality of life (EQ-5D) and Costs evaluation questionnaire) will be obtained online or by hardcopy at baseline, 6 weeks, 3 months, 6 months, 9 months and 12 months. .

DART - Surgery vs. Casting for Displaced Articular Radius Fractures in Elderly

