6.1.2 Secondary study outcomes

Response variable:

1) Change in:

- Wrist function as reported by the patient (Disabilities of the Arm, Shoulder and Hand (DASH))
- Quality of life as reported by the patient (EQ-5D)
- Costs evaluation questionnaire
- ROM (range of motion)
- Complications
- Grip strength

Explanatory variable:

- Radiographic parameters (dorsal tilt, radial inclination, radial shortening, fracture union, and posttraumatic arthritis.)
- Frailty score
- Patient reported pain catastrophizing (Pain Catastrophizing Scale (PCS))

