8. STATISTICAL ANALYSIS

To answer our primary research question, whether the change in PRWE differs between treatment groups at 1 year after trauma, we will calculate the intervention effect using a mixed model, with intervention group and baseline PRWE as fixed factors and clusters (random factors) for repeated observations within patients and patients within hospitals (the latter only if a significant random intercept of hospital is observed).. Both crude and adjusted intervention effects will be calculated on an intention-to-treat and as-treated basis.

To further investigate the intervention effect over time, we will add time as fixed effect as well as an interaction between time and intervention group. , The secondary outcome variables will be analyzed in a similar way.

In additional analyses, we will investigate confounding and effect modification of several patient and fracture characteristics.

The primary outcome will be tested for non-inferiority with respect to the predefined threshold of 14 points on the PRWE, with a one-sided 97.5% confidence interval. For superiority analyses, a two-tailed value of $p < 0.05$ is considered to be significant.

COST EFFECTIVENESS ANALYSIS (CEA)

General considerations

Within this project, we will perform an economic evaluation that is in accordance with the most recent guidelines of “The National Health Care Institute”¹⁸.

Cost analysis

An economic evaluation will be performed from a societal as well as a healthcare perspective¹⁹. When the societal perspective is applied, all costs and consequences relevant to the intervention will be taken into account irrespective of who pays or benefits, whereas solely those accruing to the healthcare sector will be taken into account when the healthcare perspective is applied²⁰. Intervention costs will be estimated using a micro-costing approach¹⁸. Cost questionnaires will be administered on a 3-monthly basis to collect data on healthcare utilization, the use of informal care, and unpaid productivity losses.

Patient outcome analysis

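### The named primary model holds only group and baseline PRWE; the planned adjusted effects have no listed covariates, and sex, dominant-hand injury and the age stratum are left unused in the decisive analysis

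*Protocol*

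**What the plan says.** Section 8 sets the primary analysis as a mixed model "with intervention group and baseline PRWE as fixed factors", with random terms for repeated observations and, only if its random intercept is significant, for hospital. The next sentence promises both crude and adjusted effects, by intention to treat and as treated. It lists no adjusting variables. The decision rule is a comparison with the "predefined threshold of 14 points on the PRWE, with a one-sided 97.5% confidence interval", and it does not say whether the crude or the adjusted estimate supplies that interval. Of other variables, Section 8 says only that, in additional analyses, "we will investigate confounding and effect modification of several patient and fracture characteristics". Secondary outcomes are to be analysed in a similar way.

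Section 5 lists what is recorded at the start: "At baseline characteristics will be collected such as sex, side, dominant hand, trauma mechanism and the frailty questionnaire". Section 6.1.2 places "Frailty score" under its explanatory variables. Sections 5 and 6.2 stratify randomisation by two age groups, and age is not among the fixed factors. The only variables that the protocol expressly says it will correct for are in Section 5: local technique, anaesthetic protocol, cast duration and vitamin C prescription. These describe how treatment is delivered. They are not patient characteristics.

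Table 1 in Section 6.3 first measures grip strength at 6 weeks.

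**The concern.** Non-inferiority here turns on the upper limit of one interval. Covariates that are fixed before allocation and predict PRWE at one year narrow that interval and remove the effect of chance imbalance. They do so reliably only if the list is set in advance in the model that decides. Under randomisation such variables are not systematic confounders in the intention-to-treat comparison. A search for confounding there tends to pick variables by how far they move the treatment estimate, and an adjusted result built that way has no assured error rate.

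Because the protocol plans both crude and adjusted effects without naming the adjusters or the decisive estimate, a reader cannot tell which interval will be compared with 14 points. The age stratum has the clearest case for inclusion: an analysis that omits a prognostic stratification factor generally gives an interval wider than the design has earned.

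Grip strength shows the gap most plainly. A model like the primary one would adjust for the baseline value, and there is none. Sex and dominant-hand injury are the recorded variables that could stand in for it.

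**Working it through.** **Inputs from the protocol.** Section 4: "Sample size calculation is based on a power of 90%, an alpha of 0.025, a standard deviation of 23 points", a 14-point difference, 20% loss and 57 per group. Section 8: margin 14, one-sided 97.5% interval. True difference taken as 0.

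**The plan's own figure.** n per group = 2 × [23 × (1.960 + 1.282) / 14]² = 56.7, so 57. This is the number before any loss. With 20% loss it would be 56.7 / 0.8 = 70.9, so 71 (72 if 57 is inflated). Enrolling 57 and losing 20% leaves 57 × 0.8 = 45.6 per group, which is the relevant base below.

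**Effect of covariates.** The protocol gives no prognostic strength, so R², the share of the remaining PRWE variance explained by the added covariates, is an assumption.

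- SE = 23 × √(1 − R²) × √(2/n)
- Power = Φ(14/SE − 1.96)
- Approximate cost of three added covariates: multiply the variance by (N − 4)/(N − 7), with N = 2n. At N = 91.2 this is 87.2/84.2 = 1.036.

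Results at 45.6 per group:

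| Model and assumed R² | Half-width, no df cost | Power, no df cost | Half-width, with df cost | Power, with df cost |
|---|---|---|---|---|
| Named model, nothing added | 9.44 | 82.8% | – | – |
| Three added, R² 0 | 9.44 | 82.8% | 9.61 | 81.5% |
| Three added, R² 0.05 | 9.20 | 84.7% | 9.36 | 83.4% |
| Three added, R² 0.10 | 8.96 | 86.5% | 9.11 | 85.3% |
| Three added, R² 0.20 | 8.44 | 90.1% | 8.59 | 89.1% |

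Against 82.8%, the net change is −1.3, +0.6, +2.5 and +6.3 points. Before the degrees-of-freedom cost the gains at R² 0.05 to 0.20 are 1.9 to 7.3 points. Break-even is R² = 3/87.2 = 0.034; with all 114 analysed it is 3/110 = 0.027. With all 57 per group analysed, power goes from 90.1% to 89.3%, 90.8%, 92.2% and 94.8% after the cost.

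**A fourth covariate.** If frailty is added, break-even at N = 91.2 rises to 4/87.2 = 0.046.

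**Grip strength.** Let p be the share of men and d the difference between the sexes in within-sex SDs. The share of variance due to sex is p(1 − p)d² / [1 + p(1 − p)d²]. Assuming p from 0.1 to 0.3 and d from 1 to 2, the extremes are 0.09/1.09 = 8% and 0.84/1.84 = 46%. Neither input is in the protocol, and the figures apply to grip as measured.

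**Timing.** Sex, injured side and hand dominance are settled by the time of injury. Section 5 asks for frailty within a week of trauma, but Table 1 puts it at the 1-week visit, not at T0. Consent, and with it randomisation, may come up to 3 weeks after trauma, and Section 4 admits patients through secondary dislocation. Frailty may therefore be recorded at about the time of allocation, and may be missing for patients who qualify late.

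**The case against.** The strongest reply is that nothing is invalid. A model with group and baseline outcome is sound in a randomised trial, and a covariate list is often left to a statistical analysis plan, which is not shown. Both points stand, so this is not an error in the estimate, and the absence of a list alone would not be a finding. What remains is that the protocol does name a model, plans adjusted effects beside it, and leaves open which one decides.

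A reader might infer several stronger things that the protocol does not support:

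- **That the analysis adjusts for baseline PRWE and nothing else.** Adjusted effects are planned; their content and status are what is missing.
- **That the precision is free.** Every gain rests on an assumed R², and about 1 power point is lost if the covariates explain nothing.
- **That frailty is known before randomisation in every patient.** Table 1 and the 3-week consent window do not guarantee it. Requiring it could mean dropping patients or imputing values.
- **That the confounding work corrupts the non-inferiority test.** It is labelled additional, so it does so only if its result becomes the adjusted estimate that decides.
- **That confounding work should be removed altogether.** The as-treated comparison is not protected by randomisation, and there it is needed.

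It is also fair to say that the fall to about 83% power comes from the sample size, since 57 does not contain the 20% loss. Covariates can offset part of that but are not its cause. Lastly, Section 4 does not say that the SD of 23 is what remains after baseline adjustment. If baseline PRWE or hospital ("outcome data will be correlated within 19 participating centers with an ICC of 0.1") already absorbs variance, power starts higher and the gain in points is smaller. Taking 10% off the variance for hospital, for example, gives 86.5% at 45.6 per group.

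**Conclusion.** The point holds as a recommended improvement in efficiency and clarity. The decisive interval is not tied to one fully specified model, and sex, dominant-hand injury and the randomisation age stratum are not committed to it. For PRWE the expected net gain at 45.6 per group is about 0.6 to 6.3 power points for an assumed R² of 0.05 to 0.20, against a loss of about 1 point at R² of 0. An R² of about 0.20 would be needed to bring power back to roughly 90%, which should not be relied on. These figures assume SD 23 as the remaining SD, a true difference of 0, 20% loss and no hospital effect. For grip strength the case is clearer in principle, because no baseline value exists, but its size rests wholly on assumed inputs and the outcome is secondary.

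**What to change.** In Section 8, before any data are seen:

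1. Define one model for the non-inferiority interval, with group, baseline PRWE, age stratum, sex and dominant-hand injury (yes/no, from side and dominant hand) as fixed effects, alongside the random terms already stated. Use the stratum as randomised, because Section 5 (75 and older) and Section 6.2 (over 75) treat age 75 differently.
2. State that this model's interval is the one compared with 14 points, and label any crude estimate as supportive.
3. Include frailty only if its completion before allocation is made a requirement.
4. Rule out choosing covariates by their effect on the estimate in the intention-to-treat comparison. Keep confounding work for the as-treated analysis, and effect modification as exploratory.
5. Name sex and dominant-hand injury as covariates for grip strength.

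This takes a few sentences in Section 8, repeated in the SAP. It needs no extra patients or visits and no new measurements. The price is three degrees of freedom, about 1 power point if the covariates turn out to explain nothing.

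### A patient random intercept would not assure the 2.5% error of a 1-year PRWE contrast, because it assumes equal variance at every visit from 6 weeks to 12 months

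*Protocol*

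**What the plan says.** Section 6.1.1 of the protocol sets the primary outcome as the PRWE 1 year after trauma. Section 5 and Table 1 (section 6.3) collect it at baseline and at 6 weeks, 3, 6, 9 and 12 months.

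Section 8 plans a mixed model with treatment group and baseline PRWE as the fixed terms and "clusters (random factors) for repeated observations within patients and patients within hospitals". The hospital level is kept only if its random intercept is significant. No random slope and no residual covariance structure is named. Time comes in a second step: "we will add time as fixed effect as well as an interaction between time and intervention group".

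The primary outcome is then "tested for non-inferiority with respect to the predefined threshold of 14 points on the PRWE", "with a one-sided 97.5% confidence interval".

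The sample size paragraph in section 4 uses "a standard deviation of 23 points and a minimal important change of 14 points". It gives no SD for any other visit and no correlation between visits.

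**The concern.** A random factor for patients, with nothing further specified, is usually fitted as a random intercept. That implies compound symmetry: one variance for the PRWE at every visit and one correlation between any two visits. The follow-up window runs from about the end of casting (4 to 6 weeks in the control group, section 5) to 1 year. Equal variance over that span is a strong assumption, and the protocol gives nothing to support it.

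The non-inferiority decision rests on one confidence limit at one visit. Under a random intercept, the standard error of the 12-month contrast comes from the variance averaged over all five visits. If the earlier visits vary less than the 12-month visit, the limit lies too close to the estimate and a truly inferior cast treatment passes too often. If they vary more, the limit lies too far out and power is lost.

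The protocol expects 20% loss to follow-up and names multiple imputation only for the economic evaluation. The mixed model is therefore the only stated means of handling missing clinical PRWE scores, which gives its covariance more weight.

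**Working it through.** **Inputs from the protocol.** Margin 14, 12-month SD 23, one-sided alpha 0.025, power 90%, 57 per group (section 4); five follow-up visits (Table 1). The SDs at the earlier visits are assumptions.

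**The plan's own figure.** n per group = 2 × 23² × (1.960 + 1.282)² / 14² = 56.7, so 57. This is the number of evaluable patients, before the stated 20% loss. If 57 are randomized and 20% are lost, about 46 per group remain. That mismatch is a separate matter; here it only explains why power is shown for both 57 and 46.

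**Formula.** With complete data and a separate mean for each group at each visit, the 12-month contrast is the difference of the 12-month means, whatever the covariance model. Its true standard error is SD₁₂ × √(2/n). The random-intercept model reports RMS × √(2/n), where RMS is the root mean square of the five visit SDs. With r = SD₁₂/RMS:

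- one-sided error at the margin = Φ(−1.96/r)
- power at a true difference of 0 = Φ(14/SE_true − 1.96/r)

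At n = 57, SE_true = 23 × √(2/57) = 4.31 and 14/4.31 = 3.25. At n = 46, SE_true = 4.80 and 14/4.80 = 2.92.

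| Assumed SDs (6 wk, 3, 6, 9, 12 mo) | RMS | r | 1.96/r | One-sided error |
|---|---|---|---|---|
| 23, 23, 23, 23, 23 | 23.00 | 1.000 | 1.960 | 2.5% |
| 19, 20, 21, 22, 23 | 21.05 | 1.093 | 1.794 | 3.6% |
| 15, 18, 20, 22, 23 | 19.81 | 1.161 | 1.688 | 4.6% |
| 31, 28, 26, 24, 23 | 26.56 | 0.866 | 2.263 | 1.2% |

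**Power.** For SDs falling from 31, power is Φ(3.25 − 2.263) = 83.8% at n = 57, against Φ(3.25 − 1.96) = 90%. At n = 46 it is Φ(2.92 − 2.263) = 74.4%, against 83%.

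**In PRWE points, n = 57.** The confidence limit should lie 1.96 × 4.31 = 8.4 points from the estimate. With SDs rising from 15, the model SE is 19.81 × √(2/57) = 3.71 (14% too small) and the distance is 7.3. With SDs falling from 31, the SE is 4.98 (15% too large) and the distance is 9.8.

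**Simulation check.** 3,000 trials per setting, 45 per arm, true difference at the 14-point margin, 12-month SD 23, REML random-intercept fit. Correlation was either constant or decaying with time, with 0% or 20% drop-out unrelated to outcome. Baseline PRWE and hospital were left out. The Monte Carlo standard error is about 0.3 percentage points.

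| Assumed SDs | 12-month contrast, time-by-group model |
|---|---|
| equal at 23 | 2.6–3.0% |
| 15, 17, 19, 21, 23 | 4.8–5.9% |
| 30, 27, 25, 24, 23 | 1.3–1.8% |

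For the last two patterns the formula gives 5.1% (RMS 19.21, r = 1.197) and 1.4% (RMS 25.92, r = 0.887), in line with the simulation. In the same settings, the model as written, without time terms and with the same difference at every visit, had an error of 2.1–3.0% throughout.

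**The case against.** Four points can be made on the other side.

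1. **The text does not say that random intercepts are the only covariance terms.** The one random intercept it names is for hospital. This stands as to wording: a random patient intercept is the natural reading, not a stated one. But section 8 does name a device for within-patient dependence, and an SAP that follows it literally would carry the assumption forward.

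2. **Covariance structure is commonly SAP material.** Degrees-of-freedom methods and a convergence fall-back are, and their absence is no fault of the protocol. The point here is narrower: the device that section 8 does name would not protect the error rate of a 1-year test.

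3. **The primary model as written is not affected.** This stands. It has no time term, so its group effect is an average over visits, and the simulated error of that average stayed near nominal. But an average over visits is not the 1-year outcome of section 6.1.1. The only model in the plan that gives a 1-year effect is the time-by-group model, and the variance problem arises there.

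4. **The visit SDs are assumed.** This stands. The figures also leave out baseline adjustment and hospital. With baseline in the model, the residual SDs by visit are what count, and the protocol does not give them.

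A reader might go further and infer that the error rate is not 2.5%, or that it is inflated. The documents do not support either. Equal SDs give 2.5%, and falling SDs make the test conservative. A reader might also blame the single correlation. The simulation does not bear that out: with equal SDs and decaying correlation the error was 2.6–2.8%, with or without drop-out. Unequal variances drive the effect.

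**Conclusion.** The point holds in a conditional form. If the 1-year effect is taken from the time-by-group model with a random patient intercept, the nominal one-sided 2.5% is not assured. Over the assumed SD patterns in the formula, it runs from about 1.2% (SDs falling from 31 to 23, with power of 84% instead of 90% at 57 per arm) to about 4.6% (SDs rising from 15 to 23). It is 2.5% with equal SDs. The protocol's single SD does not show which way the variances run.

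The conclusion rests on three things: the natural reading of the patient random factor, a test based on a 12-month contrast, and visit SDs that differ materially from the 12-month SD. It is a point that should be put right before analysis; it does not show that the trial's error rate is wrong.

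**What to change.** State in section 8, or in the SAP, that the 14-point non-inferiority test uses the cast-minus-ORIF contrast at 12 months from a model with categorical visit, group, group-by-visit and baseline PRWE. Specify an unstructured within-patient covariance over the five follow-up visits, or at least a structure with a separate variance at each visit, in place of the random patient intercept. The 12-month standard error is then not tied to the variance at the earlier visits, whichever way the variances run. The same change gives the test the 1-year effect that section 6.1.1 calls for; a new covariance structure alone would not do that.

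The cost is one sentence and no extra data. An unstructured matrix for five visits has 5 × 6 / 2 = 15 parameters, to be estimated from at most 114 × 5 = 570 scores, or about 500 after losses. If it does not converge, a simpler structure that keeps visit-specific variances (heterogeneous Toeplitz, for example) is enough. The order of fall-backs and the degrees-of-freedom method can be left to the SAP.

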6.2 Randomization, blinding and treatment allocation

Upon obtaining informed consent, patients will be randomized into either the intervention group (open reduction and internal fixation) or the control group (closed reduction and plaster immobilization). In order to avoid any imbalance between treatment groups, patients will be randomized in 2 strata using a block randomization. Two strata according to age: 65-75 and over 75 years of age. Randomization will be performed by means of a computerized randomization.

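### The primary model leaves out the age stratum used for randomisation and lets a weak significance test decide whether hospital is modelled

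*Protocol*

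**What the plan says.** **Randomisation.** Allocation is by individual patient, in blocks, stratified by age only. Section 5 (All groups) defines the strata as "Two strata according to age: 65-75 and 75 and older". Section 6.2 has "Two strata according to age: 65-75 and over 75 years of age". Under section 5 a 75-year-old belongs to both strata; under section 6.2 only to the younger.

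**Primary model.** Section 8 names group and baseline PRWE as fixed factors. The random effects are repeated observations within patients, and patients within hospitals, "the latter only if a significant random intercept of hospital is observed". Age stratum is not named. The section also announces crude and adjusted effects, but does not list the adjustment covariates or say which effect is primary.

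**Decision rule.** The result is compared with the "predefined threshold of 14 points on the PRWE", "with a one-sided 97.5% confidence interval".

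**Sample size.** Section 4 says "outcome data will be correlated within 19 participating centers with an ICC of 0.1". Section 4 (Feasibility) speaks of at least 6 clinics.

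**Elsewhere.** The cost-effectiveness part of section 8 plans multilevel analyses for possible clustering without any significance condition.

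**The concern.** Blocking within age strata makes the arms alike in age. If age predicts the 1-year PRWE, the treatment estimate varies less than a model without the stratum believes, so the reported interval is too wide.

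The hospital rule raises a different problem. It makes the form of the primary model depend on a test in the trial data. With about five or six patients per centre that test has little power, so a non-significant result says little about whether hospitals differ. The plan has reason to expect that they do: it assumes an ICC of 0.1, and it leaves technique, anaesthesia, cast duration and vitamin C to local protocol.

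At stake is whether the limit compared with 14 comes from one model fixed in advance, and a small amount of precision.

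**Working it through.** **Inputs from the protocol.** One-sided alpha 0.025, power 90%, SD 23, margin 14, ICC 0.1, 19 centres, 114 randomised, 20% loss (114 × 0.8 ≈ 91 evaluable).
**Assumptions not in the protocol.** True difference 0, a 5% level for the hospital test, the within-patient correlation, and the size of any age effect.

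**1. The plan's own figure.** The plain non-inferiority formula gives 2 × 23² × (1.960 + 1.282)² / 14² = 56.7, so 57 per group. This already equals the stated number before any loss (57 / 0.8 = 71.25, so 72) and before any clustering factor.

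**2. Chance that hospital is significant when the ICC really is 0.1.** For k equal centres of m patients, the one-way F statistic is inflated by q = 1 + m × 0.1/0.9. The chance of significance is P(F > F_crit / q) on k − 1 and N − k degrees of freedom.

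| Centres | Evaluable | m | F_crit | q | Chance kept |
|---|---|---|---|---|---|
| 19 | 114 | 6.0 | 1.713 | 1.667 | 0.44 |
| 19 | 91 | 4.8 | 1.749 | 1.532 | 0.33 |
| 6 | 114 | 19.0 | 2.298 | 3.111 | 0.60 |
| 6 | 91 | 15.2 | 2.322 | 2.685 | 0.51 |

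The protocol does not name the test, so a REML likelihood-ratio test was also simulated (2,500 to 3,000 trials per scenario). The lower figure of each pair uses a chi-square with 1 df, the upper the mixture reference distribution.

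- 19 centres, 114 evaluable: 0.31 to 0.42 with equal centres, 0.37 to 0.46 with unequal centres.
- 19 centres, 91 evaluable: 0.21 to 0.30 with equal centres, 0.28 to 0.37 with unequal centres.
- 6 centres, 91 or 114 evaluable: 0.37 to 0.54.

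Over all 19-centre results hospital is kept in 0.21 to 0.46 of trials and so dropped in 0.54 to 0.79. With 6 centres, both tests together give 0.37 to 0.60 kept.

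**3. Repeated measures.** Table 1 has five follow-up PRWE scores. With within-patient correlation r, the ICC of a patient's mean score is 0.1 / (r + (1 − r)/5): 0.167 for r = 0.5 and 0.109 for r = 0.9. With 19 centres and r from 0.5 to 0.9, the chance of keeping hospital is 0.26 to 0.70; it exceeds one half only at the lower correlations.

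**4. Precision.** With unrestricted individual allocation across centres, a share (N − k)/(N − 1) of the treatment contrast lies within centres. Relative to a model without hospital, the information is that share / 0.9 plus the remaining share / (1 + (m − 1) × 0.1).

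- N = 114: 0.841/0.9 + 0.159/1.5 = 1.040, so the SE ratio is 1/√1.040 = 0.980.
- N = 91: 0.800/0.9 + 0.200/1.379 = 1.034, so the SE ratio is 0.983.

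The simulation with equal centres agrees: mean SE 4.28 without hospital and 4.18 with it (114 evaluable), and 4.79 and 4.69 (91 evaluable).

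**5. Power and type I error (19 centres, ICC 0.1).**

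| Evaluable | Centres | Power: never | Power: pre-test | Power: always |
|---|---|---|---|---|
| 114 | equal | 0.900 | 0.902 | 0.907 |
| 114 | unequal | 0.895 | 0.903 | 0.908 |
| 91 | equal | 0.817 | 0.830 | 0.842 |
| 91 | unequal | 0.822 | 0.826 | 0.826 |

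Always fitting hospital gains 0 to 1.2 points over the pre-test; each power estimate near 0.83 has a simulation error of about 0.7 points. One-sided type I error at a true difference of 14 is 0.022 to 0.029 under all three rules, with a simulation error of about 0.003.

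**6. Age stratum.** If the stratum explains a share R² of the outcome variance, the true SE is √(1 − R²) times the SE of the model that omits it: 0.99 for 2%, 0.97 for 5%, 0.95 for 10%. With equal strata differing by d points, R² = (d/2)²/23², which is 1.2% for d = 5 and 4.7% for d = 10. Any overlap with baseline PRWE lowers these shares.

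**The case against.** The strongest defence is that little is lost. Hospital is not a randomisation factor, patients are randomised individually, and both omissions err towards an interval that is too wide, which makes non-inferiority harder to claim. The promised adjusted effects may include age, and listing covariates is commonly left to an analysis plan. All of this stands as to size. It does not remove the point, because the protocol is not silent here: it names the fixed factors and lays down a data-dependent rule for the random effect.

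Three stronger readings are tempting, and the documents do not support them.

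- *Dropping hospital gives false claims of non-inferiority.* A reader might carry this over from cluster-randomised trials. Under individual allocation the error rate stays near 2.5% whichever rule is used.
- *The analysis discards a clustering allowance built into the sample size.* Section 4 says that clustering was taken into account, but 57 per group is the plain figure with no visible allowance to lose. That is a separate matter for the sample size section.
- *The rule will usually drop hospital.* This holds for 19 centres and the 1-year score alone. The planned model uses repeated observations, and the centre count is also given as at least 6; in either case the chance is nearer even.

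**Conclusion.** The point holds as one of pre-specification with a small cost in precision. The primary model omits the factor used to stratify randomisation, and whether hospital enters is settled by a test with low power. On the plan's own ICC of 0.1 and 19 centres, with the 1-year score alone, hospital would be dropped more often than not. A trial that drops it has an SE about 2% larger, and the plan gives up about 1 point of power at most compared with always fitting it. The loss from omitting the age stratum depends on an age effect that the protocol does not give: 1% to 3% of the SE if the stratum explains 2% to 5% of the variance, and none if age is not prognostic. Type I error is not at risk.

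The two age definitions contradict each other. The wording affects only patients aged exactly 75, but the stratum cannot be fitted as randomised until it is settled.

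**What to change.** In section 8, state that the primary model always includes the age stratum as a fixed effect and hospital as a random intercept, regardless of significance.

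In sections 5 and 6.2, give one non-overlapping definition of the age strata, identical to the one in the randomisation program.

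The cost is one sentence and one corrected definition. The model gains one fixed parameter. The hospital variance may be estimated at zero (in about 11% to 17% of the simulated 19-centre trials at an ICC of 0.1); the fit then reduces to the model without hospital, so the text should say that this is accepted and does not trigger a change of model.
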